2.5 Summary Table of Objectives and Endpoints

Objectives	Endpoints	Timepoint(s) of evaluation of this endpoint (if applicable)
Primary Objective	As above	Maximum 12 weeks following enrolment
Secondary Objectives	As above	Maximum 12 weeks following enrolment

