8.3 Statistical Analysis

Interim monitoring & internal pilot

We will monitor recruitment, statistical assumptions and safety at 6 months and formally review 12 months recruitment into the internal pilot. During the first 12 months, our targets are for gradual opening of at up to 10 centres (although more can be opened if possible), 700 recruited for randomisation-1 and 400 for randomisation-2. At this stage, stopping guidance will be based on ability to recruit, and on discussion with the independent trials steering committee.

Our independent data monitoring committee will provide stopping guidance based on interim futility or demonstrated superiority analyses when at least 50% of our overall sample size for randomisation-1 has provided primary outcome data. They will also consider the underlying assumptions for randomisation-2 and make recommendations regarding continuation of randomisation-2 at this point.

We will monitor recruitment, statistical assumptions and safety regularly throughout the trial. There will be an independent Trial Steering Committee (TSC) and Data and Ethics Monitoring Committee (DMEC). The first 12 months of recruitment will be an internal pilot with an emphasis on ability to recruit, with targets at this stage being 700 patients recruited from at least 10 centres and obtaining primary outcome data on 80% of all participants randomised up to 4 months prior to data-extraction (accounting for expected timeframe: 3 months for conduct of MRI and biopsy and histology results to be made available followed by up to 30 days to transfer data to the database).

Proposed length of internal	I pilot phase: 12 month	S
-----------------------------	-------------------------	---

Pilot Trial Targets Red Amber Green

IP7-PACIFIC Protocol No: 22CX7488	Imperial College London	V3.0 18 th December 2023
-----------------------------------	-------------------------	-------------------------------------

% Recruitment threshold	<50%	50 - 99.9%	≥100%
Recruitment rate / site / month	2.8	2.9-5.8	≥5.8
Number of sites opened	5	6-9	≥10
Total number of participants recruited	<350	350-699	≥700
% Primary outcome data threshold	<40%	40-80%	≥80%
(all randomised 60 days prior to data extraction)			

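### The pilot's 80% outcome-completeness target is set on a 4-month cut-off in the text but a 60-day cut-off in the table, and the 60-day version counts on-schedule participants as missing

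*Protocol*

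**What the plan says.** Everything at issue is in the interim monitoring and internal pilot part of Protocol section 8.3. It states that "The first 12 months of recruitment will be an internal pilot".

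- **Text.** One pilot target is "obtaining primary outcome data on 80% of all participants randomised up to 4 months prior to data-extraction". The reason given is "3 months for conduct of MRI and biopsy and histology results to be made available", with a further allowance of at most 30 days for moving the data into the trial database.
- **Table.** The row "Primary outcome data threshold" is red below 40%, amber at 40-80% and green at 80% or more. Its qualifier is "all randomised 60 days prior to data extraction".
- **Pathway timing elsewhere.** Section 2.5 gives the time point for the primary objective as "Maximum 12 weeks following enrolment". The visit schedule in section 5.4 places MRI and biopsy in weeks 1-8 and biopsy results in weeks 2-12.
- **Accrual.** For the pilot year, "our targets are for gradual opening of at up to 10 centres", with 700 participants to be recruited.
- **Continuation rule.** The summary after the table depends on recruitment only: at least 700, 350-699, or fewer than 350.

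**The concern.** The same 80% target is applied to two different groups of participants, and nothing in the protocol reconciles them. The text's cut-off comes with a rationale. The table's has none and is shorter than the pathway that the protocol allows. Under the table, someone biopsied in week 8 and awaiting histology, fully on protocol, enters the denominator with no outcome and counts against completeness.

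The row is meant to tell the steering committee whether outcome data are being lost. That matters here because section 8.3 counts missing outcomes as no clinically significant cancer in the primary analysis. A row that mixes lost data with results still pending does not answer the question, and two readers could grade the same pilot green and amber.

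**Working it through.** **Step 1: the plan's own lag.** 3 months + 30 days = 90 + 30 = 120 days, about 4 months, as the text says. Using section 2.5 instead: 12 weeks = 84 days, and 84 + 30 = 114 days. Both exceed 60 days, and 84 does so before any transfer time. A biopsy at the end of week 8 (day 56) leaves 60 - 56 = 4 days for histology and data entry.

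**Step 2: inputs and assumptions.** From the protocol: a 12-month pilot, 700 recruits, gradual site opening. Assumed, because the protocol does not fix them: extraction at day 365, the shape of accrual, and enrolment and randomisation on the same day. The worst case takes every outcome to arrive at day 120 with none lost.

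**Step 3: table score under perfect return.** With A(t) the number randomised by day t,

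score = A(365 - 120) / A(365 - 60) = A(245) / A(305).

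For even accrual, A(t) is proportional to t. For gradual opening, the rate rises linearly until day r and is then flat, so A(t) is proportional to t²/(2r) up to r and to t - r/2 afterwards.

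| Accrual | Calculation | Score |
|---|---|---|
| Even | 245/305 | 80.3% |
| Sites open over 3 months (r = 91) | 199.5/259.5 | 76.9% |
| Over 6 months (r = 182) | 154/214 | 72.0% |
| Over 9 months (r = 273) | 109.9/168.5 | 65.2% |
| Over 12 months (r = 365) | (245/305)² | 64.5% |

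In whole months, the first and last rows are 8/10 = 80% and (8/10)² = 64%. Taking 4 months as 121.7 days, even accrual gives 243.3/305 = 79.8%.

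In participants, under even accrual: 700 × 305/365 = 585 are in the denominator and 700 × 245/365 = 470 have data. About 115 on-schedule people therefore count as missing.

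With the text's 4-month denominator, perfect return scores 100% under every accrual pattern.

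**Step 4: relaxing the worst case.** "Ramp" here would be sites opening over 12 months.

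| Assumption | Even | Ramp |
|---|---|---|
| Half of the 60-120 day band has data | 0.80 + 0.20 × 0.5 = 90% | 0.64 + 0.36 × 0.5 = 82% |
| All outcomes at day 114 | 251/305 = 82% | (251/305)² = 68% |
| All outcomes at day 84, no transfer time | 281/305 = 92% | (281/305)² = 85% |
| 30% complete by day 60, 70% at day 120 | 0.3 + 0.7 × 0.803 = 86% | 0.3 + 0.7 × 0.645 = 75% |
| Results spread evenly over 2-12 weeks plus 0-30 days transfer (simulated) | 96% | 93% |
| Worst-case lag, extraction at month 14 | 10/12 = 83% | (10/12)² = 69% |
| Worst-case lag, extraction at month 16 | 100% | 100% |

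Under the ramp, the row reaches 80% once a fraction f of the band has data, where 0.64 + 0.36f = 0.80, so f = 0.16/0.36 = 44%.

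**The case against.** The inconsistency itself is not in dispute. The case against making much of it has three parts.

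- **No written decision depends on this row.** Section 8.3 ties stopping guidance to ability to recruit and to discussion with the steering committee, and the continuation rule uses recruitment counts alone. No action is attached to amber or red on completeness. This stands. A reader might infer that the row is a go/no-go criterion that could halt the trial, but the protocol does not say so.
- **The 64% to 80% range is a worst case.** It needs extraction at month 12 and no data from anyone in the 60-120 day band. Section 5.4 allows biopsy on the day of MRI, section 5.2 cites a 28-day diagnosis target, section 8.1 assumes that 70% are recommended for biopsy, so about 30% may have no histology to wait for, and both 12 weeks and 30 days are upper limits. This also stands. A miss is possible, not certain, and even accrual alone leaves the row at about 80%.
- **The site-rate row is not shown to be wrong.** A reader might infer that 5.8 per site per month contradicts gradual opening, since 700/(10 × 12) = 5.83 takes ten sites as open all year. But 5.8 × 10 × 12 = 696, which matches the 700 target after rounding, and section 8.2 speaks of up to 10 pilot centres for 12 months. Read as a nominal average, the rate, site and total rows agree. The protocol gives no opening schedule from which a contradiction could be calculated.

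None of this reconciles the two cut-offs or makes 60 days long enough for the stated pathway.

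**Conclusion.** The protocol states one completeness target on two incompatible denominators, and the table's version is shorter than the protocol's own time to outcome. This is plain from the wording and needs no assumption.

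The size does need assumptions. With extraction at month 12 and outcomes arriving only at the 4-month limit, perfect data return scores about 80% under even accrual, with no room for any real loss, and about 64% to 77% under gradual opening, which is amber. With shorter lags or later extraction the row can be green: 82% to 90% if half of the band has data, and 93% to 96% if results are spread over the whole permitted window.

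The consequence is a possible misleading amber on data return. The sample size, the primary analysis and the written continuation rule are unaffected. A lesser flaw in the same row is that amber (40-80%) and green (80% or more) both include exactly 80%, which is where perfect return falls under even accrual.

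**What to change.** In the section 8.3 table, change the qualifier on the completeness row to *all randomised at least 4 months before data extraction*, to match the text and its rationale. Set the amber band to *40% to <80%* so that each result has one colour.

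The cost is a wording change to one table row. The check will rest on fewer participants: about 470 instead of 585 with even accrual of 700 and extraction at month 12. In return, the 80% threshold measures data return only, whatever the pace of site opening.

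### The internal pilot's 80% outcome-completeness target has two denominators, 4 months in the text and 60 days in the traffic-light table, and only the 4-month one fits the protocol's own timetable.

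*Protocol*

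**What the plan says.** Section 8.3 (interim monitoring and internal pilot) states the target in the text as "obtaining primary outcome data on 80% of all participants randomised up to 4 months prior to data-extraction". It gives the reason in brackets: "3 months for conduct of MRI and biopsy and histology results to be made available followed by up to 30 days" for data transfer. The natural reading is participants randomised 4 months or more before extraction, because the stated reason makes sense only on that reading.

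The traffic-light table that follows has a row headed "Primary outcome data threshold", with red below 40%, amber 40-80% and green at 80% or more. The row's population is "all randomised 60 days prior to data extraction".

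Section 2.5 gives the time point of the primary endpoint as "Maximum 12 weeks following enrolment". The visit schedule (Section 5.4) puts MRI and biopsy in weeks 1-8 and biopsy results at visit 4, in weeks 2-12.

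On the pilot itself, "The first 12 months of recruitment will be an internal pilot", with a target of "700 patients recruited from at least 10 centres" and gradual opening of centres.

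**The concern.** The same 80% figure is applied to two populations. The text waits until every participant on schedule should have data. The table admits participants at day 60, although results may come as late as week 12 (day 84) and data transfer may take 30 days more (day 114). The row therefore counts some on-schedule participants as missing, and more of them when centres open gradually and recruitment falls later in the year.

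The completeness signal has a purpose. The primary intention-to-treat analysis treats a missing outcome as no clinically significant cancer (Section 8.3, main study clinical outcomes analysis), so the steering committee needs to tell real data loss from outcomes not yet due. The 60-day row mixes the two, and the same data can give one answer under the text and another under the table.

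**Working it through.** **The protocol's own window.** Three months plus 30 days is 3 × 30.44 + 30 = 121.3 days, and 4 months is 4 × 30.44 = 121.8 days. The text's window reproduces. Sixty days follows from no stated component.

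**Size of the band not yet due.** Inputs from the protocol: 700 participants over 12 months. Assumptions: extraction at month 12, months of 30.4 days (T = 364.8 days), and either uniform recruitment (k = 1) or a linear ramp (k = 2) to represent gradual opening. The number randomised at least d days before extraction is N(d) = 700 × ((T − d)/T)^k.

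| Recruitment | N(60) | N(120) | 60-120 days out | Share of table denominator |
|---|---|---|---|---|
| Uniform | 585 | 470 | 115 | 20% |
| Linear ramp | 489 | 315 | 173 | 35% |

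**Score on the table row.** Let c be completeness at 4 months, f the share of participants in the 60-120-day band who will eventually report and already have, and r = N(120)/N(60), which is 0.803 (uniform) or 0.645 (ramp). Then

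table % = c × [r + (1 − r) × f].

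**A value of f from the visit schedule.** Assume results are spread evenly over weeks 2-12 (days 14-84) in those biopsied and weeks 1-8 (days 7-56) in those not biopsied. Assume 70% biopsied (the share recommended for biopsy in Section 8.1) or 100%, and a data lag either uniform on 0-30 days or always 30 days. Worked example, all biopsied, lag 30 days, uniform recruitment: the share with data at day a is (a − 44)/70. It rises from 0.229 at day 60 to 1 at day 114, averages 0.614 over those 54 days, and is 1 for the last 6. So f = (54 × 0.614 + 6)/60 = 0.65. The ramp weights the band slightly towards recent recruits, which lowers f a little.

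| Recruitment | Biopsied | Lag | f | Table % at c = 80% | at c = 82% | at c = 90% | c needed for green |
|---|---|---|---|---|---|---|---|
| Uniform | 70% | 0-30 d | 0.86 | 77.7 | 79.7 | 87.5 | 82.3% |
| Uniform | 100% | 0-30 d | 0.81 | 77.0 | 78.9 | 86.6 | 83.1% |
| Uniform | 70% | 30 d | 0.72 | 75.6 | 77.5 | 85.1 | 84.6% |
| Uniform | 100% | 30 d | 0.65 | 74.5 | 76.4 | 83.8 | 85.9% |
| Ramp | 70% | 0-30 d | 0.85 | 75.7 | 77.6 | 85.2 | 84.5% |
| Ramp | 100% | 0-30 d | 0.80 | 74.3 | 76.2 | 83.6 | 86.1% |
| Ramp | 70% | 30 d | 0.71 | 71.7 | 73.5 | 80.7 | 89.2% |
| Ramp | 100% | 30 d | 0.64 | 69.7 | 71.5 | 78.4 | 91.8% |

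A pilot at 80-82% by the text is amber on the table in all eight scenarios. A pilot at 90% is green in seven of the eight. None comes near the red limit of 40%.

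**The case against.** The strongest case on the other side is about consequence. A reader might take this row for a formal go/stop threshold and infer that the 60-day window could halt the trial. The protocol does not support that. Section 8.3 bases stopping guidance on ability to recruit and on discussion with the steering committee, and its closing summary sets the continue, improve and stop rules on recruitment counts alone (700 or more, 350-699, below 350). No action is attached to amber on the completeness row. This stands, and it limits the severity.

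A reader might also infer a large fall in the score by supposing that half, a quarter or none of the band has reported. At 90% completeness that would give 81%, 77% and 72% under uniform recruitment, and 74%, 66% and 58% under the ramp. Such fractions are low against the protocol's schedule. Biopsy may be on the same day as the MRI (Section 5.4), centres work towards a 28-day diagnosis target (Section 5.2), about 30% are not expected to be recommended for biopsy (Section 8.1), and anyone on schedule has data by day 114. Nor do recent recruits dominate the denominator. They are 35% of it even under the ramp.

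The extraction date is not stated either. If data were extracted 4 months after pilot recruitment ended, both denominators would hold all 700 participants and the discrepancy would have no effect. Finally, the error is in the cautious direction, since a false amber prompts a closer look.

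None of this reconciles the two windows. A named target with its own cut-offs is still defined twice, and one definition conflicts with the reason given for the other.

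**Conclusion.** Wrong as written, low severity. The text and the table give incompatible denominators for one target, and the protocol's timetable supports only 4 months. If extraction is at about month 12, participants whose outcome may not yet be due form about 20-35% of the table's denominator. The row then shows amber for a pilot that only just meets the text target. Completeness at 4 months must reach about 82-92%, depending on the scenario, before the row turns green.

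The size rests on the assumed extraction date, recruitment shapes and evenly spread delays. The contradiction itself rests on none of them. The harm is a misleading amber and possibly misdirected effort on data return. Estimands, error rates, power and the final analysis are not affected.

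**What to change.** Change the population in the table row to participants randomised at least 4 months before data extraction, so that it matches the text and its stated reason. Make the change before the pilot review, so that the denominator is not chosen with the data in view.

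The cost is one table cell and somewhat fewer participants in the completeness figure: about 315-470 instead of 490-585 if extraction is at month 12.

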2.3 Primary Endpoint

Randomisation-1: bpMRI versus mpMRI

Proportion of clinically significant cancers, defined as any amount of Gleason >/=3+4 (ISUP Grade Group >/=2) on biopsy, detected in the randomised population of patients at risk.

Randomisation-2: Visual-registration targeting versus image-fusion targeting

Proportion of clinically significant cancers, defined as any amount of Gleason >/=3+4 (ISUP Grade Group >/=2) on biopsy, detected in the randomised population of patients biopsied for a suspicious MRI.

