3. STUDY DESIGN

IP7-PACIFIC incorporates two linked RCTs which will test whether bpMRI and image-fusion make a difference if used in clinical practice, across multiple centres, without the incorporation bias inherent in paired-cohort studies [Stabile et al, 2018]. Our design provides economies of scale and scope compared to addressing these research gaps with two separate RCTs.

Since bpMRI is an abbreviated examination, clinicians and patients require reassurance that it is no worse than mpMRI. Therefore, we plan a non-inferiority evaluation. The second randomisation will involve co-enrolment of a subgroup of the first randomised group i.e., patients referred for biopsy following a positive MRI result. To justify the extra cost for the technology, we would expect image-fusion to detect more clinically significant cancers than visual-registration targeting.

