- Prior prostate cancer diagnosis at any time-point. Patients on active surveillance will have differing prior probabilities of clinically significant prostate cancer to those referred with a clinical suspicion and are therefore excluded.
- Any absolute contraindication to MRI, gadolinium or biopsy. Patients with bilateral hip prostheses are excluded. These prostheses often cast a large imaging artefact over the prostate area on MRI and radiologists prefer a mpMRI scan because the diffusion images

can be particularly affected. In other words, there is lack of equipoise in these patients for randomisation between mpMRI and bpMRI.

- Contraindication to performing a biopsy guided by a transrectal ultrasound probe
- Unable to give informed consent to the study

Randomisation-2: Visual-registration targeting versus image-fusion targeting

Inclusion

Suspicious finding on mpMRI or bpMRI from randomisation-1 requiring targeted biopsy (MRI categories 3, 4 or 5)

Exclusion

As above for randomisation 1 Patient refusal for biopsy

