In summary, if at least 700 (100%) patients are recruited in the pilot, we would expect the TSC to recommend continuation of the trial (in line with NIHR guidance regarding green threshold). If the pilot recruits less than 350 patients (<50%), then this indicates a recommendation for stopping unless there is a very good reason for delay and a convincing solution can be employed. If the pilot recruits 350-699 (50-99%) then, in discussion with the TSC and funder, measures to improve recruitment may be needed in the main trial. We shall use the % targets (100%, 50-99%, <50%) to inform study management setting site-specific targets, depending on the expected recruitment as declared by each of our pilot sites. We shall monitor site recruitment regularly as part of study management and if sites are underperforming or delayed in set-up, we shall consider opening sites from a reserve list.

Randomisation-2 will be stratified by arm allocated in randomisation-1. Potential effects of co-enrolment are likely small but will be monitored. Comparisons will be adjusted for trial arm of the other trial and if we were to anticipate an increase in SEs by 5% from using adjusted effect estimates, we would maintain an adequate level of power (>80%) in our respective randomised comparisons.

Main study clinical outcomes analysis

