For each randomisation, the number and proportion of clinically significant cancers detected in the randomised population will be reported by trial arm. Group differences will be quantified by the risk difference with two-sided confidence intervals at a level appropriate to the significance level pre-specified in the sample size. Detection rates will be compared by trial arm using mixed models with adjustment for trial arm allocation of co-enrolled trial and random effect by centre. The treatment effect coefficients will be presented with confidence intervals and associated p-value. The primary analysis will be conducted on an intention-totreat (ITT) basis, where patients with missing outcomes are assumed not to have clinically significant prostate cancer. A modified ITT analysis will be performed excluding patients who did not complete the diagnostic tests, and for the non-inferiority comparison a per protocol analysis including only those undergoing randomly assigned interventions. A pre-specified statistical analysis plan will be drafted detailing intended analyses for primary and secondary outcomes. It will be approved by the IDMC and agreed prior to analysis.

Cost-effectiveness analysis

A within trial cost-effectiveness analyses will estimate the incremental cost per true positive detected and incremental cost per correct diagnosis. Estimates of diagnostic performance will be based on the trial analysis and costs will be estimated from the NHS and PSS perspective using a micro-costing approach for tests. Deterministic (to explore plausible alternatives e.g., quantity of resources used or unit costs) will be combined with stochastic

IP7-PACIFIC Protocol No: 22CX7488	Imperial College London	V3.0 18 th December 2023
-----------------------------------	-------------------------	-------------------------------------

sensitivity analysis (used to explore statistical imprecision in estimates of costs, effects and cost-effectiveness).

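### Adjusting the bpMRI versus mpMRI comparison for the randomisation-2 arm conditions on a consequence of the scan and changes what is estimated; the error can go either way

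*Protocol*

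**What the plan says.** Section 8.3 states one adjustment rule for both comparisons. Under the internal pilot text: "Comparisons will be adjusted for trial arm of the other trial". Under the main clinical outcomes analysis, introduced as applying to each randomisation, detection rates are compared "using mixed models with adjustment for trial arm allocation of co-enrolled trial and random effect by centre". The only consequence considered is precision, a possible "increase in SEs by 5% from using adjusted effect estimates", after which power is said to stay above 80%.

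The two randomisations are nested, not crossed. Section 3 describes "co-enrolment of a subgroup of the first randomised group i.e., patients referred for biopsy following a positive MRI result". Section 4.1 makes the entry condition "Suspicious finding on mpMRI or bpMRI from randomisation-1 requiring targeted biopsy (MRI categories 3, 4 or 5". Section 8.3 adds: "Randomisation-2 will be stratified by arm allocated in randomisation-1".

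The randomisation-1 endpoint in section 2.3 is clinically significant cancer "detected in the randomised population of patients at risk", so it counts every patient randomised to a scan, biopsied or not.

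Just before the mixed-model sentence, section 8.3 says that group differences will be expressed as risk differences with confidence intervals matched to the sample-size significance level. It does not say whether these are adjusted, or whether they or the model coefficient decide non-inferiority.

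**The concern.** The rule is right in one direction only. For randomisation 2, MRI arm is a pre-randomisation stratification factor. For randomisation 1, having a randomisation-2 arm at all is a result of the assigned scan. Conditioning on it removes or distorts whatever part of the MRI effect works by changing which scans are called suspicious. The protocol regards that step as an outcome of the MRI arm: non-inferiority in the proportion recommended for biopsy is a secondary objective (section 2.2) and biopsy rate is called a key secondary outcome (section 11.9).

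The covariate is also undefined for many patients. On the protocol's own planning figures (70% recommended for biopsy, a further 10% attrition), 1 − 0.70 × 0.90 = 37% would have no randomisation-2 arm. Each way of handling them gives a different estimand. At stake is the trial's main decision, whether a 5-point loss has been excluded.

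**Working it through.** **Reproducing the plan's figure.** Inputs from section 8.1: 38% in both arms, margin 5 points, one-sided 0.05, 90% power.
n per arm = 2 × 0.38 × 0.62 × (1.645 + 1.282)² / 0.05² ≈ 1,615, or 3,230 in total. This matches, and it is an unadjusted comparison of all randomised patients. Raising the SE by 5% gives power 87.3%, consistent with the protocol's statement of more than 80%. The precision argument is therefore correct; the estimand is what it leaves out.

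**What the adjusted coefficient estimates.** Take a linear model with MRI arm and three-level status k (not in randomisation 2, visual, fusion). Let a_k and b_k be the shares of the mpMRI and bpMRI arms in level k, and d_k the within-level difference in detection. Then

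adjusted effect = Σ w_k d_k / Σ w_k, with w_k = a_k b_k / (a_k + b_k).

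Differences between arms in the shares themselves, which are part of the scan's effect, do not enter except through the weights.

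**Assumptions not in the protocol.** mpMRI suspicious in 70%, all of whom enter randomisation 2; 2% detection outside randomisation 2; mean yield among mpMRI-suspicious patients (0.38 − 0.30 × 0.02)/0.70 = 53.4% (visual 48.4%, fusion 58.4%), so that the mpMRI arm totals 38%. The bpMRI suspicious rates are varied. Simulations use 1,615 per arm, a linear probability model with robust SE and no centre effect. Non-inferiority is declared when the one-sided 95% lower limit exceeds −5 points.

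**Worked cases, three-level covariate.**

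- *Fewer suspicious scans, same yield.* A 33% total needs a bpMRI suspicious rate of (0.33 − 0.02)/(0.534 − 0.02) = 60.3%. All d_k = 0, so the adjusted effect is 0.0 against a true −5.0.
- *Essentially every missed scan a cancer (bpMRI 65%).* bpMRI yield = (0.33 − 0.35 × 0.02)/0.65 = 49.7%, so d = −3.74 points in the visual and fusion levels and 0 outside. Weights: outside 0.30 × 0.35/0.65 = 0.162; each biopsy level 0.35 × 0.325/0.675 = 0.1685. Effect = −3.74 × 0.337/(0.337 + 0.162) = −2.5.
- *Same suspicious rate, lower yield.* bpMRI yield = (0.33 − 0.006)/0.70 = 46.3%, d = −7.14. Effect = −7.14 × 0.35/(0.35 + 0.15) = −5.0, correct.
- *bpMRI adds only false positives (75%), no true difference.* Yield = (0.38 − 0.005)/0.75 = 50.0%, d = −3.43. Weights: outside 0.30 × 0.25/0.55 = 0.136; two biopsy levels 0.362 together. Effect = −3.43 × 0.362/0.498 = −2.5 against a true 0.

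**Simulated chance of declaring non-inferiority.**

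| Scenario (bpMRI suspicious rate) | True effect | Unadjusted | Three-level covariate | Fusion = 1, all others = 0 | Randomisation-2 patients only |
|---|---|---|---|---|---|
| Fewer suspicious scans, same yield (60.3%) | −5 | 4.8% | 96% | 27% | 74% |
| Missed scans essentially all cancer (65%) | −5 | about 5-6% | 51% | 13% | 14% |
| Fewer suspicious scans, higher yield (58%) | −5 | 5.0% | 99.9% | 39% | 95% |
| Mixed: fewer scans and lower yield (66%) | −5 | 5.1% | 38% | 11% | 8% |
| Lower yield only (70%) | −5 | 5.2% | 5.1% | 4.7% | 0.4% |
| Same yield, larger loss (50.6%) | −10 | 0.0% | 96% | 0.4% | 71% |
| False positives only (75%) | 0 | 90% | 50% | 83% | 19% |

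With 10% instead of 2% detection outside randomisation 2, the first row becomes 4.9%, 94%, 30% and 74%. With zero detection outside and suspicious rates of 63.3% against 55%, the three-level figure is 98%. With zero detection outside and false positives only (63.3% to 70%), it drops from 91% unadjusted to 19%.

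**The case against.** Three points on the other side have force.

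First, section 8.3 does promise a risk difference with confidence intervals. The margin is an absolute difference and the sample size is unadjusted, so this is a natural quantity on which to judge non-inferiority. If it is unadjusted and decides, the harm is limited to a misleading secondary coefficient. But the protocol says neither. It attaches the p-value to the model coefficients and says that comparisons will be adjusted. The ambiguity stands.

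Second, a reader might infer that the adjustment always biases the test towards non-inferiority. The documents do not support that. The bias takes that direction when bpMRI calls fewer scans suspicious. The protocol's stated worry is the opposite: the primary objective is to detect cancer without more biopsies (section 2.1), and the clinician survey asked about a margin for more men being biopsied (section 11.8). The pooled figures in the Background give bpMRI slightly higher sensitivity (90% against 86%) and slightly lower specificity (70% against 73%), neither difference significant. If bpMRI adds suspicious calls, the error works against bpMRI.

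Third, the coding of patients without a randomisation-2 arm is ordinary SAP detail, and the size of the error depends on it. That is true of size. It does not rescue the rule: each of the three codings tried departs from the endpoint in all randomised patients once suspicious rates differ between arms. Keeping only randomisation-2 patients also discards much of the intention-to-treat population.

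**Conclusion.** The point holds as a fault in a rule that the protocol fixes. Applied to randomisation 1, the co-enrolment adjustment conditions on a consequence of the MRI arm, and its coefficient does not in general estimate the effect on detection in all randomised patients at risk.

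For a true 5-point loss arising from fewer suspicious scans, false non-inferiority ranges from about 13% to over 99% across the codings and scenarios tried, against about 5% unadjusted. The mixed case at 66% gives 8% to 38%. If bpMRI only adds false positives, correct declaration with the three-level covariate falls from about 90% to 20-50%. If only yield among suspicious scans falls, the three-level model is unbiased, while restriction to randomisation-2 patients exaggerates the loss. These figures rest on assumed suspicious rates, assumed detection outside randomisation 2 and a simplified linear model without centre effects.

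The stronger statement that the trial's main conclusion would be invalid does not follow. It would require that the adjusted coefficient decides non-inferiority and that bpMRI shifts the suspicious rate, and the protocol establishes neither.

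**What to change.** In section 8.3, and in the SAP to match:

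- Limit the co-enrolment adjustment to randomisation 2, adjusted for MRI arm.
- For randomisation 1, state that non-inferiority is judged against −5 points from the risk difference in all randomised patients, with no adjustment for randomisation-2 arm or entry. Keep centre in the model; baseline covariates are optional.
- Do not use an MRI-arm effect split by targeting technique as a check on co-enrolment. It makes the same post-randomisation selection: with zero detection outside randomisation 2 and a true −5.0, the fusion stratum gave +0.2. If reported, label it as descriptive among patients with suspicious scans only.

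The cost is a sentence or two of text. It needs no extra patients or data, and the sample size of 3,230 already assumes the unadjusted comparison.
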